#### 14.1.3 Methods

Specimens for cytogenetic and FISH analysis must be performed for the required time points at each institution's preferred CLIA-approved cytogenetic and FISH laboratory. A copy of the Cytogenetic Form from the Case Report Forms in Medidata Rave® should be printed and submitted to the institution's preferred cytogenetic lab along with the contact information for the CRP and the specimen; the Cytogenetic Form can be found in the A041701 All Forms Packet on the Alliance and CTSU websites. An editable PDF of the forms can also be obtained by contacting the Alliance Cytogenetics Committee Office (see below). Use of an Alliance approved cytogeneticist is encouraged but not required; a list of Alliance-approved cytogeneticists can be found on the study-specific webpage on the Alliance and CTSU websites.

Cytogenetics samples obtained are required to be submitted at the following timepoints:

- Prior to initiation of therapy
- 1st complete remission (if diagnostic specimen is abnormal)
- End of consolidation (if cytogenetics are abnormal at CR)
- Relapse.

Required processing of specimen includes 24 or 48 hour culture of bone marrow specimen (unstimulated blood culture required if marrow tap is dry), G-banding, and analysis of first 20 analyzable metaphase spreads.

#### Submission of Cytogenetic Samples

After local review has been performed, the designated local cytogeneticist will complete the Cytogenetic Form and provide the required karyotype, metaphase images, and FISH information (if applicable) to the institution. The responses provided by the local cytogeneticist on the Cytogenetic Form will be entered in Medidata Rave® by site staff, and the required supporting documentation will be uploaded in Medidata Rave® for the use of the Alliance Cytogenetic Committee Office. The cytogenetic data from the prior to registration time point should be entered in Medidata Rave® within 28 days of patient registration; data for all other time points should be entered within 14 days of institution's receipt of local review results.

- Karyotypes and metaphases must be submitted via Medidata Rave®. Include the karyotype description or clone number in the bottom of the high resolution electronic image with arrows placed indicating abnormalities. Images (karyotype, metaphase, and FISH) are preferred to be submitted together in one PowerPoint (PPT) file. If this is not possible, individual .jpeg or .tiff files are accepted. Photocopies, faxes, and low-resolution PDF scans of karyotypes and metaphases will not be accepted. Write "Random Loss" next to the homologue when appropriate. If one copy (or both copies) of a given chromosome is overlapped or distorted, please submit a partial karyotype from another cell from the same clone showing both homologues of this chromosome intact, so that the reviewers are able

to evaluate each chromosome pair without distortion or overlap in at least two cells from the same clone.

- For any abnormal, non-clonal cell not on the "List of Specific Abnormalities" ([Appendix I](#)), submit the International System for Human Cytogenetics Nomenclature (ISCN), karyotype is not required.
- Two karyotypes of each abnormal clone and the corresponding metaphase spreads are required for submission. For any abnormal, non-clonal cell related to a clone, or for any abnormal, non-clonal cell not related to a clone and not on the "List of Specific Abnormalities" ([Appendix I](#)), submit the ISCN, but do not submit karyotype.
- If case is abnormal, non-clonal (has one or more of the characteristic abnormalities specified on the list), enter the ISCN of each cell and provide a karyotype and corresponding metaphase representing each type of abnormality present.
- If case is normal, submit two karyotypes and corresponding metaphase spreads for the normal clone. Submit karyotypes and associated metaphases for any abnormal non-clonal cell present in a normal case if it contains an abnormality on the "List of Specific Abnormalities" ([Appendix I](#)).
- If the presence of a constitutional abnormality is suspected, the laboratory should perform analysis necessary to confirm or refute such suspicion (e.g., PHA-stimulated cultures of peripheral blood) and submit the results.
- Unsuccessful cytogenetic studies at the required time points are still required to be submitted.
- For samples of peripheral blood only abnormal outcome will be accepted.
- Follow-up will continue for required cytogenetic samples until relapse, withdrawal of consent, or death for up to 15 years.

#### **Optional Additional Procedures:**

- Direct preparations of AML specimens are acceptable only if the case is abnormal.
- Unstimulated 24-48 hour cultures of peripheral blood.
- Standard PHA-stimulated cultures of peripheral blood.
- Other banding procedures.
- Counting and/or analysis of additional metaphase spreads.
- Submission of additional karyotypes.
- Appropriate metaphase or interphase fluorescence in situ hybridization (FISH) analyses. Abnormal FISH results are encouraged to be submitted. Provide FISH information and two images (in the PowerPoint file with karyotypes and metaphases (preferred) or as individual .jpeg or .tiff files) for each assay performed.

### **Central Karyotype Review**

Karyotypes will be sent to the Central Karyotype Review Committee if the material is adequate in terms of numbers of metaphases and required numbers of karyotypes.

#### **14.1.4 Analyses**

Analyses will be conducted using the analysis dataset used for the analysis of the clinical endpoints to ensure consistent data is reported for the primary and secondary endpoints (e.g. data associated with censoring, proper inclusion of crossover data, and data to be excluded in cases of consent withdrawals for follow-up and correlative studies). In this study, we plan to group the patients into ELN 2017 risk categories using centrally reviewed cytogenetics, see Section 14.1.3: Central Karyotype Review. We will then use that data as a factor in analyses as it is well known that cytogenetics play a role in outcome of patients. Since we are focusing on these ELN 2017 risk categories, we will be able to avoid making false conclusions due to multiple testing. For correlative studies, we will use per family error rate by setting the expected false discovery rate to 1. Using this we will be able to determine the multiplier needed to adjust for various hypotheses contained in the objectives of the study.

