## 5.0 STUDY CALENDAR

The pre-study testing intervals are guidelines only. Laboratory and clinical parameters during treatment are to be followed using individual institutional guidelines and the best clinical judgment of the responsible physician. It is expected that patients on this study will be cared for by physicians experienced in the treatment and supportive care of patients on this trial.

When calculating days of tests and measurements, the day a test or measurement is done is considered Day 0. Therefore, if a test were done on a Monday, the Monday one week later would be considered Day 7.

	Baseline*	Induction	End of Induction	Consolidation	End of Treatment	Follow-up**
Tests & Observations						
History and physical	X	X		X	X	X
Performance Status	X					
Height and weight	X	X		X		
MUGA or ECHO	X					
ECG	X					
Adverse Event Assessment	X	X	X	X	X	
Laboratory Studies						
FLT3 Mutation analysis	X					
CBC with differential	X	X(2)	X	X(2)		X
Serum Creatinine	X	X(3)		X(3)		
Bilirubin, AST, ALT, Alk. Phos.	X	X(3)		X(3)		
INR, PTT, fibrinogen	X					
Uric Acid	X					
LDH	X					
Molecular genetic testing	X(1)					
Cytogenetics	X		B		B	B
Staging						
BM biopsy/aspirate	X(4)	A	X		X	C
Correlative studies: For patients who consent to participate						
Bone marrow and blood samples	Prior to treatment, end of induction, end of consolidation, and relapse. See Section 6.2.					

\* Baseline studies are to be completed  $\leq$  14 days prior to registration.

\*\* Follow-up should occur at least every 2 months (+/- 14 days) in year 1, every 3 months (+/- 14 days) in year 2, then every 6 months (+/- 30 days) until 5 years from registration (See [Section 12.3](#)). Cytogenetics reports for applicable time points should be submitted until 15 years following registration.

- 1 Molecular testing is to be performed according institutional standards but should include testing for mutations in *FLT3*, *NPM1*, *CEBPA*, *RUNX1*, *ASXL1*, *IDH1*, *IDH2* and *TP53* to allow classification of patients by 2017 WHO criteria and stratification by 2017 ELN genetic risk classification [23].
- 2 CBC should be performed daily while inpatient and at least twice weekly until hematopoietic recovery. Please submit induction lab tests and results in Rave from either the labs drawn at the end of the cycle, or the lab that that will correspond to the disease response.

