### **6.1.2 Supporting Documentation to be Submitted to the Alliance**

This study requires supporting documentation for diagnosis, response, and relapse. Supporting documentation will include CBC, bone marrow pathology, molecular genetic testing, cytogenetics, and FISH reports (if applicable) which must be submitted at the following time points:

Diagnosis: CBC, bone marrow pathology, molecular genetic testing, cytogenetics, and FISH reports (if applicable)

Day 14: Bone marrow pathology

End of induction: CBC, bone marrow pathology, cytogenetics, and FISH reports (if applicable)

End of treatment: CBC, bone marrow pathology, cytogenetics, and FISH reports (if applicable)

Time of relapse: CBC, bone marrow pathology, cytogenetics, and FISH reports (if applicable)

Supporting documentation is to be submitted via Rave.

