## 14.1 Cytogenetic Correlative Science (Alliance A041701)

### 14.1.1 Background

Cytogenetic analyses in acute myeloid leukemia (AML) and acute lymphoblastic leukemia (ALL) have revealed a great number of non-random chromosome abnormalities. In many instances, molecular studies of these abnormalities identified specific genes implicated in the process of leukemogenesis. The more common chromosome aberrations have been associated with specific laboratory and clinical characteristics, and are now being used as diagnostic and prognostic markers guiding the clinician in selecting the most effective therapies. Specific chromosome aberrations and their molecular counterparts have been included in the World Health Organization classification of hematologic malignancies, and together with morphology, immunophenotype and clinical features are used to define distinct disease entities. The European Leukemia Net Classification also uses specific chromosome aberrations and molecular information to classify patients.

Pretreatment cytogenetic findings have been repeatedly shown to be among the most important, independent prognostic factors in AML. Consequently, cytogenetic analyses are considered mandatory for analyzing outcome of many clinical trials and are currently used to stratify patients for different types of therapy. For instance, based on the European Leukemia Net (ELN) 2017 risk categories (Döhner et al, Blood, 2017; 129:424-47), patients with inv(16)(p13.1q22) or t(16;16)(p13.1;q22) and t(8;21)(q22;q22.1) are associated with a better risk and survival. Patients with t(6;9)(p23;q34.1), t(v;11q23.3), t(9;22)(q34.1;q11.2), inv(3)(q21.3q26.2) or t(3;3)(q21.3;q26.2), -5 or del(5q), -7, -17/abn(17p) and complex or monosomal karyotype are associated with adverse risk and poor survival. The remaining patients, those with t(9;11)(p21.3;q23.3) or cytogenetic abnormalities not classified as favorable or adverse are associated with intermediate risk and survival.

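### Section 14.1.4 builds ELN 2017 risk categories from cytogenetics and names no mutation input, although the protocol says the classification uses mutations and collects them for that purpose

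*Combined protocol and SAP*

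**What the plan says.** Section 14.1.4 (Analyses, under the cytogenetic correlative study) gives the rule: "we plan to group the patients into ELN 2017 risk categories using centrally reviewed cytogenetics". Its only cross-reference is to the Central Karyotype Review paragraph of Section 14.1.3. The stated use is: "We will then use that data as a factor in analyses as it is well known that cytogenetics play a role" in patient outcome. The section gives the grouping a second job, as protection against multiplicity: "Since we are focusing on these ELN 2017 risk categories, we will be able to avoid making false conclusions due to multiple testing".

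Three other places bear on what an ELN 2017 category needs:

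- Section 14.1.1 (Background): "The European Leukemia Net Classification also uses specific chromosome aberrations and molecular information to classify patients".
- Section 5.0 (Study Calendar), footnote 1: "Molecular testing is to be performed according institutional standards but should include testing for mutations in" eight listed genes, FLT3 among them. The purpose given is "to allow classification of patients by 2017 WHO criteria and stratification by 2017 ELN genetic risk classification".
- Section 6.1.2 puts molecular genetic testing among the reports that sites must submit at diagnosis, through Rave.

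Section 14.2 plans central molecular profiling of a required baseline sample, subject to a later amendment. Section 14.2.3 fixes the methods only once enrollment is complete.

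**The concern.** The protocol describes a classification with two kinds of input, requests and collects both, and then writes an assignment rule that names only one. A variable built by that rule would not be the classification whose name it carries.

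What is at stake is the meaning of every result reported by ELN 2017 category. A patient whose mutation results would move the category sits in the wrong group, so outcome differences between groups could be distorted, and readers would take the label at face value in a trial described as an FDA registration study. The multiplicity argument in Section 14.1.4 also depends on one fixed definition of the categories. If a karyotype-only version and a combined version could both be reported as ELN 2017, that protection weakens unless the choice is made before outcomes by category are seen.

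**Working it through.** The plan states no figure on this point, so there is nothing to reproduce. The check is a comparison of the texts.

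1. **Inputs named in the rule.** Section 14.1.4 names centrally reviewed cytogenetics, points to karyotype review, and justifies the factor by the prognostic role of cytogenetics. It mentions no gene, mutation report or molecular result.

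2. **Inputs the protocol says the classification uses.** Section 14.1.1 names chromosome aberrations and molecular information. Steps 1 and 2 therefore differ by one input.

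3. **Is the missing input available?** Footnote 1 of the Study Calendar requests it for ELN 2017 stratification (and for WHO classification), and Section 6.1.2 makes the report part of the diagnosis submission. Availability is good but not guaranteed: testing follows institutional standards, and the footnote says only that the panel should include the listed genes.

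4. **Does another section supply the link?** Section 14.2.1 expects central profiling to complement cytogenetics and refine prognostic groups. Section 14.2.4 plans models of molecular markers, alone and combined with other variables. Neither says that mutation results enter the categories of Section 14.1.4.

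5. **Does the background fill the gap?** After its statement on molecular information, Section 14.1.1 describes the ELN 2017 groups by karyotype only. Its residual group is t(9;11) together with other abnormalities: "cytogenetic abnormalities not classified as favorable or adverse are associated with intermediate risk and survival". A normal karyotype is not expressly placed in any of the three groups, although Sections 2.3.1 and 14.1.2 name it as a group to be analyzed.

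6. **Which analyses could be affected?** Sections 4.7 and 13.1 stratify randomization by age, performance status, and de novo versus secondary or therapy-related AML. ELN risk is not among these factors, and Section 13.2.1 does not put it in the EFS or OS log-rank tests. The multivariable models of Section 14.3.4 list cytogenetic risk as a covariate, not ELN risk. What remains is the correlative work under Section 14.1, prognostic-factor analyses, and any other analysis that uses the ELN grouping.

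7. **How many patients?** This would need the fraction of enrolled patients whose category changes when mutation results are added, and the documents do not give it. Section 3.3.1 excludes activating FLT3 mutations above a stated threshold, which removes part of the effect. The other seven listed genes (8 − 1 = 7) are not exclusion criteria.

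**The case against.** The best defense is that Section 14.1.4 does not say cytogenetics alone. It sits in the cytogenetics section and may only be naming the source of the karyotype component, meaning central rather than local review. Read with Section 14.1.1, footnote 1 and Section 6.1.2, the authors may well intend to combine the inputs. This stands in part: a decision to ignore mutations is not stated. But a rule that names one input, cross-refers only to karyotype review and cites only cytogenetics as its reason will be applied as a karyotype rule unless it is changed.

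Second, molecular prognosis is covered elsewhere. Section 13.2.2 lists molecular genetic features among the predictors of CR, EFS, DFS and OS, and Section 14.2.4 models molecular markers. That is true, and it limits the harm: mutation information is not lost to the trial. It does not make the ELN variable correct.

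Third, local mutation results are imperfect. Section 14.2.1 itself describes heterogeneity among commercial sequencing assays, and with accrual closed a test that was never done may be recoverable only from banked material. This stands, and it is why the remedy needs a precedence rule and an unknown class.

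Two stronger readings are tempting. A reader might infer that a large, quantifiable share of patients will be misassigned. The documents give neither the mutation frequencies nor the genes that change a category, so any count would rest on outside assumptions. A reader might also infer that results could not be set against the ELN rows in the background tables of the earlier uproleselan trial (Tables 1 and 2). Those tables say only ELN, with no edition or method, so nothing can be concluded either way.

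**Conclusion.** The point holds as a conflict between the assignment rule and the protocol's own account of the classification. If Section 14.1.4 is followed as written, the variable is a cytogenetic risk group labeled ELN 2017, and each patient whose mutation results would change the category is misclassified. This rests on reading the rule as complete, which is the plain reading because no section adds an input.

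The number affected cannot be derived. The reach is limited to correlative, prognostic-factor and any other ELN-based analyses. A reader might infer that the primary comparison, or a specified ELN-adjusted treatment effect, is compromised. The documents do not support that: ELN risk is in no stratum and no primary test, and no ELN-adjusted treatment comparison is specified. The change should be made, but it does not bear on the main EFS or OS conclusions.

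**What to change.** Amend Section 14.1.4 as follows:

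- Assign ELN 2017 risk from the centrally reviewed karyotype combined with the baseline mutation results submitted under Section 6.1.2.
- Prespecify which mutation result prevails when the local report and the central result under Section 14.2 differ.
- Code a patient as ELN unknown when the category depends on a gene for which no result is available.
- State where a normal karyotype falls.
- Analyze the karyotype-only grouping separately and call it cytogenetic risk, the term already used in Section 14.3.4.

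At minimum, rename the Section 14.1.4 variable cytogenetic risk. Either change should be settled before analyses by this grouping are run, so that the definition is not chosen with outcomes in view.

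The cost is SAP wording and abstraction of reports the sites already submit. No new patients or samples are needed. The drawback is an unknown class whose size depends on how complete the local panels were. The documents do not show how large it would be, so it should be tabulated by arm.

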### **14.2 Molecular Genetic Analysis**

An amendment for the molecular genetic testing will be submitted to CTEP, NCI for review and approval according to NCTN guidelines. Amendments to the protocol and/or proposals for use of banked bone marrow or blood samples will include the appropriate background, experimental plans with assay details, and a detailed statistical section. Samples for testing will not be released for testing until the appropriate NCI approvals have been obtained.

#### **14.2.1 Background**

Large scale DNA sequencing studies have identified over 250 recurring somatic mutations in AML and have defined the genomic landscape of the disease [26]. Understanding the genetics of AML has led to refinements in disease classification, informs prognosis, and has identified potential targets for therapeutic intervention.

Molecular genetic testing using either single gene or next generation sequencing assays has become a routine and essential part of the clinical care of patients with AML. As a corollary, interpretation of clinical trial data in AML requires and understanding of the genetic context of the patient population. In clinical practice, however, heterogeneity exists in commercially available next generation sequencing assays for AML due to differences including sequencing platform, library generation, sequencing platform, sequencing coverage, read depth and variant interpretation. Furthermore, because the field of molecular genetics is a rapidly evolving area in AML with constant refinements in gene panels and sequencing technology. Genetic information that would be considered clinically meaningful and relevant in the future at the time of study analysis may not be currently available through routine clinical testing for patients enrolled earlier in the course of the study.

For these reasons, a baseline, pretreatment bone marrow and blood sample will be required from all patients to allow for centralized genetic molecular profiling. The information obtained will complement cytogenetic analysis to refine prognostic groups and response to treatment.

### 14.2.2 Objectives

- To prospectively obtain specimens required for a baseline molecular characterization of patients treated on study.
- To determine the frequency of specific gene alterations.
- To determine the association of specific gene alterations with pretreatment characteristics and clinical outcomes.

### 14.2.3 Methods

The specific details of the molecular genetic testing for the samples will be determined after all patients are enrolled and will reflect the best available information about the molecular genetics of AML and sequencing technology at the time of analysis.

### 14.2.4 Analysis

The objectives are to examine three types of associations: (1) association of molecular features with pretreatment characteristics, (2) association among molecular markers, and (3) the association of molecular markers with clinical endpoints, such as CR, DFS, EFS, CIR, and OS. The type of analysis will be determined based on the nature of the variables analyzed. Fisher's exact and Wilcoxon rank-sum tests will compare categorical and continuous variables, respectively. To analyze multiple factors related to the probability of achieving CR, logistic regression models will be constructed. For DFS, EFS, and OS, Kaplan-Meier curves will be constructed and the log-rank test will be used to examine the impact of single molecular markers on outcome. In addition, combinations of molecular markers along with other potentially important variables will be examined in multivariable analyses, using Cox regression.

